## 1.0 BACKGROUND AND HYPOTHESES

### 1.1 Clinical Significance

Dental fear and anxiety (DFA) is a common emotional experience that most often develops in early childhood and adolescence. In their systematic review, Cianetti et. al, compared the prevalence of dental fear and anxiety in children according to a variety of available measurement tools and scales. Their results showed that between 10-29% of children experience DFA. It is more common in females, and its prevalence decreases with age. DFA poses several problems. The first is that most patients who experience DFA also exhibit behavior problems in the dental setting. Dental anxiety is one of the main reasons people avoid seeking dental care, and children who have high dental anxiety have a higher caries experience. Additionally, Moore et. al demonstrated in a survey of dentists that one of the biggest causes of stress for a dentist is managing their anxious patients, as these patients are often unpredictable, more time consuming, and require more skill to manage.

Currently, the American Academy of Pediatric Dentistry (AAPD) recognizes and promotes the usage of many behavior management techniques including communicative, pharmacological, and protective stabilization methods. When a child is healthy and cooperative enough to allow dental work to be completed, basic techniques should be used to avoid potential risks associated with stabilization, sedation, and general anesthesia. Some of these basic techniques, outlined in the AAPD guidelines, include tell-show-do, ask-tell-ask, memory restructuring, positive pre-visit imagery, and distraction.

Distraction has been explored for improving the experience of pediatric dental patients in a variety of ways. Aminabadi et. al, showed that distraction via verbal stimulation during an intraoral injection had significant results in decreasing reported pain in pediatric patients. Another study, exploring audio-only and audio-visual distraction via devices mounted to the dental chair or ceiling showed that anxiety and behavior improved with audio-visual distraction as compared to the control. More recently, virtual reality systems, have been explored for use as a distraction method in healthcare settings.

Virtual reality is defined as “a three-dimensional environment generated by means of computer technology that creates a sense of immersion in the user, transporting the individual to appealing and interactive settings”. Several studies have shown that virtual reality is an effective intervention in healthcare settings including needle-procedures in children, treatment of burn victims, and patients experiencing chronic pain.

Piskorz et. al assessed the effect of virtual reality on stress and pain management during venipunctures in pediatric patients (age 7-17 years), and showed that the children who experienced virtual reality during the procedure reported significantly lower pain and stress, and that there was no correlation with age . Walther et. al reported that 100% of children in their study (ages 7-16) stated that they would prefer virtual reality as a distraction option during the venous cannulation procedure, compared to the control group who received standard behavior guidance techniques (topical numbing cream, positioning, and distraction) . In their review of literature, Li et. al report that analgesia plus virtual reality is more effective than analgesia alone in children ages 5-18 undergoing burn care.

In the dental setting, researchers are exploring the effect of virtual reality on patient compliance, patient anxiety, and long-term memories of treatment. Lahti et. al showed that a brief pre-operative immersive virtual reality experience in a peaceful landscape resulted in a significant decrease in anticipatory anxiety in adult patients prior to dental treatment compared to the control group . Another study simulated a dental experience with adult patients in a laboratory resembling a dental office, with an audio system providing instructions of tasks to complete, for example, to open their mouth and keep it open . This study reported that patients who experienced virtual reality during the simulation were more compliant with instructions, and those who reported dental anxiety showed greater reduction in memory vividness of the experience, when VR was used than compared to the control group . No currently published studies have assessed the direct effect of the use virtual reality systems the behavior of pediatric dental patients during restorative dental treatment.

## 1.2 Hypothesis

It is hypothesized that the use of virtual reality technology as a distraction technique will improve behavior in pediatric and adolescent patients undergoing dental sealant placement.

It is hypothesized that the use of virtual reality technology during dental sealant placement will be more effective in decreasing pain and dental anxiety when compared to basic behavior guidance techniques.

## 2.0 OBJECTIVES AND PURPOSE

- 2.1 The primary objective of this study is to investigate the effect of virtual reality on the behavior of pediatric patient when compared to basic behavior guidance techniques during dental sealant placement.

- 2.2 A secondary objective is to evaluate the effect of virtual reality pain experienced by a patient when compared to basic behavior guidance techniques during dental sealant placement.
- 2.3 An additional objective is to evaluate the effect of virtual reality on reduction of anxiety when compared to basic behavior guidance techniques during dental sealant placement.

### 3.0 STUDY DESIGN

This study is a randomized controlled trial with a crossover design. The study will be carried out at the USC Herman Ostrow School of Dentistry graduate pediatric dental clinic and Children's Dental Health Clinic in Long Beach Memorial Hospital. Patients who are visiting the clinic for a comprehensive or periodic dental exam and are found to require two or more dental sealants (at least one sealant per side) will be recruited for the study. The study subjects will include children ages 6-17 who are ASA I or II (as defined by the American Society of Anesthesiologists classification system). Nitrous oxide for anxiolysis during dental treatment is not indicated for research participants due to signs of cooperative behavior during initial exam. Cooperative behavior is determined through Frankl Score being an F3 or F4. Participant and legal guardian must deny any use of nitrous for dental sealant placement before VR study is introduced and patient is recruited as a prospective participant. The proposed sample size for this pilot study is 40 participants.

This is a split mouth design in which children who are enrolled in the study will serve as both the experimental group and their own control. After the child and parent are scheduled dental sealant appointment, they will be randomly assigned to receive the virtual reality system as a distraction technique for the first half or the latter half of the appointment. During the time where virtual reality is not used, traditional basic behavior guidance techniques will be used, as is the standard of care.

The virtual reality system being used for research purposes is the RelieVR by Applied VR which includes the goggle headset only. The VR experience will be an immersive experience where the child will interact with the system and navigate their way through a game which will involve bright colors, cartoon-like characters and settings with age-appropriate content. The VR system will be worn for approximately 5-10 minutes during sealant application.

Each patient will serve as their own control. The control sample will include basic behavior guidance techniques only. Informed consent will be obtained from the patient or guardian and documented in the patient's record prior to placement of dental sealants and use of virtual reality.

The heart rate will be analyzed at specific steps of the procedure including:

- Baseline (patient sitting in the chair prior to treatment)
- During sealant placement with Virtual Reality distraction
- During sealant placement with basic behavior guidance techniques
- Post Operative (patient sitting upright in chair, 5 minutes after procedure)

Patient's anxiety will be evaluated by heart rate. Each child enrolled in the study will wear a pulse oximeter throughout the duration of the entire treatment appointment. The patient's heart rate (beats per minute) will be verbally announced by the provider at the time points listed above. The use of the pulse oximeter, recording of the heart rate will be used for research purposes only, and will be transferred to a protected data sheet by the person who is examining the video recording of the appointment at a later date.

The behaviors, as they happen in real time during the dental appointment, will be handled according to the standard of care and the patient and parent's comfort level. For example, when a child is moving to the point where it interferes with the provider's ability to render treatment safely, the appointment will be aborted and rescheduled with nitrous oxide, moderate sedation or general anesthesia. If a child cries, this will be addressed according to the standard of care, such that a crying child is given the chance to express any pain/concern/requests for modification to treatment, but some children use crying as a coping mechanism and are able to complete dental treatment safely and atraumatically. A child who falls asleep will be allowed to sleep, given that their breathing is being monitored and the child can respond to verbal commands or tactile stimulus, when necessary, as is the standard of care. This is in line with the typical behavior management of children receiving dental care and is outlined in the AAPD Guidelines for Behavior Management (20). All of these behaviors are normal responses to children and are dealt with regardless of participation in this research study.

Additionally, after sealant application with VR and control, the provider will assign the patient a Frankl behavior score, and record it in the patient's chart, as is the standard of care. All patient behavior is routinely documented in the patient chart using the Frankl behavior score, regardless of participation in this research study. The provider will also complete a Healthcare Provider Questionnaire through Qualtrics. (Appendix A. Figure 4)

This is a pilot study. Data analyzed will be changed in heart rate between baseline and sealant placement using virtual reality or behavior guidance technique.. No statistical analysis will be conducted except mean and range. Other factors will also be analyzed including timing of virtual reality intervention (1st vs. 2nd half of the appointment), age, gender, previous dental experience, and average amount of "screen time" a child is allowed per week.

The demographic factors will be collected from the patient's medical chart. Ethnicity will not be collected.

The parent will be asked “how many hours of “screen time” (TV, computer, video games, tablet use), would you say that your child is allowed per week?” and this will be recorded with their coded Study ID number during the recruitment phase. See Coded ID and data sheet in section 13.2. Parents will also be asked to complete a satisfaction survey after the Virtual Reality appointment and the Standard of Care appointment. (Appendix A. Figure 3.1 and 3.2)

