#### 10.0 CRITERIA FOR EVALUATION AND ENDPOINT DEFINITIONS

The outcome status (behavior) of all eligible patients will be reported.

Frankl Score: Patient's behavior as rated by the dental provider within one of the following categories: 1= definitely negative, 2= negative, 3= positive, 4= definitely positive. This scale is routinely used by dentists and documented in the patient chart.

Behavior, and anxiety will be scored at the following time points:

- Baseline (patient sitting in the chair prior to treatment)
- During sealant placement with virtual reality distraction
- During sealant placement with basic behavior guidance
- Post Operative (patient sitting upright in chair, 5 minutes post completion of dental sealant placement)

Anxiety: Measured by change in heart rate at outlined points (above) during restorative procedure.

Completion of Dental Treatment: Was the treatment able to be completed, or was the appointment aborted due to patient cooperation, complication with virtual reality system, or any other reason.

Parent Satisfaction Survey: Will be evaluated post treatment for the Virtual Reality and standard of care. Satisfaction questions will be asked on a scale on a scale of 1 to 10. (Appendix A. Figure 3.1 and 3.2)

Healthcare Provider Questionnaire: Will be obtained after each session, completed by the provider performing treatment. (Appendix A. Figure 4)

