#### 12.0 DATA COLLECTION AND MONITORING

Each patient will be given a study ID number (the number labeled on the exterior of the random envelope they are assigned) and the physical master list of all participants will be kept in a separate location from the data (in a binder located at Children's Dental Health Clinic at Long Beach Memorial Resident Room or USC pediatric graduate clinic). See Appendix A.

A Frankl score will also be assigned to each patient by the providing dentist at the end of each appointment and recorded in the Dentrix software where patient electronic health records are kept at the Children's Dental Health Clinic at Long Beach Memorial or Axium software at USC's pediatric graduate clinic.

After consenting to participation in the research, the patient and parent will be asked the patient's average weekly "screen time" which will be recorded in the Dentrix/Axium treatment note for their initial exam appointment.

Each patient will wear a pulse-oximeter during dental treatment appointments. The heart will be reported verbally at outlined steps during the procedure and analyzed at a later date. The person viewing the video will record the verbally reported heart rate and at each step into the data collection sheet (see Appendix B).

The providing dentist will ask the patient at the end of the treatment, for research purposes, if any adverse side effects were experienced during VR use and include it in the Dentrix/Axium treatment note for that appointment.

The data from the parent satisfaction survey and healthcare provider questionnaire will be obtained electronically through Qualtrics and the data will be transferred to an excel sheet stored in USC OneDrive. There will be no paper versions of the data collected. The excel sheet will be kept and secured until the end of the study, at which point it will be deleted. See Appendix B.

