**Parent Satisfaction Survey – Standard Care**

1. What did you and your child do to prepare for the procedure?  
\_\_\_\_\_

2. Was the procedure what you expected?  
1 2 3 4 5 6 7 8 9 10  
Not at all Somewhat Definitely  
\_\_\_\_\_

3. How well do you think the procedure went?  
1 2 3 4 5 6 7 8 9 10  
Not at all well Moderately well Extremely well  
\_\_\_\_\_

4. How well do you think your child's pain was managed?  
1 2 3 4 5 6 7 8 9 10  
Not at all well Moderately well Extremely well  
\_\_\_\_\_

5. Do you think more could have been done to make your child's pain better?  
1 2 3 4 5 6 7 8 9 10  
Nothing more Some things more A lot more  
\_\_\_\_\_

6. Did your child have any distress (anxiety or worry) before or during the procedure?  
☐ YES ☐ NO

7. If your child had any distress (anxiety or worry), how well do you think it was managed?  
1 2 3 4 5 6 7 8 9 10  
Not at all well Moderately well Extremely well  
\_\_\_\_\_

8. How satisfied are you with the procedure as a whole?  
1 2 3 4 5 6 7 8 9 10  
Not at all Moderately Extremely  
\_\_\_\_\_

9. What are your thoughts and feelings about the procedure?  
\_\_\_\_\_  
\_\_\_\_\_

Figure 4- Healthcare Provider Questionnaire

STUDY ID # \_\_\_\_\_ DATE \_\_\_\_\_ **HEALTHCARE PROVIDER QUESTIONNAIRE**

1. How cooperative was the child during the procedure?  
1 2 3 4 5 6 7 8 9 10  
not at all moderately extremely

2. How much pain do you think the child experienced?  
1 2 3 4 5 6 7 8 9 10 ☐ N/A  
no pain moderate pain worst pain

3. How satisfied were you with the management of the child's pain during the procedure?  
1 2 3 4 5 6 7 8 9 10 ☐ N/A  
not at all moderately extremely

4. How much anxiety do you think the child experienced?  
1 2 3 4 5 6 7 8 9 10 ☐ N/A  
no anxiety moderate anxiety worst anxiety

5. How satisfied were you with the management of the child's anxiety during the procedure?  
1 2 3 4 5 6 7 8 9 10 ☐ N/A  
not at all moderately extremely

6. If the child played the virtual reality game, do you think that it helped the child during the procedure?  
☐ Yes ☐ No ☐ Not Applicable  
Please explain: \_\_\_\_\_

7. Would you like to use the virtual reality game again with other patients?  
☐ Yes ☐ No ☐ Not Applicable  
Please explain: \_\_\_\_\_

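### The treating provider announces the research-only heart rate during each half and then rates behavior, pain and anxiety, so these ratings are not independent of the heart-rate outcome

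*Protocol*

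**What the plan says.** Protocol Section 3.0 states "Patient's anxiety will be evaluated by heart rate" and lists four time points: baseline, during sealant placement with VR, during sealant placement with BBG, and five minutes after the procedure. The value "will be verbally announced by the provider at the time points listed above". The same section says that "recording of the heart rate will be used for research purposes only".

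Section 3.0 then says that, after sealant application under each condition, "the provider will assign the patient a Frankl behavior score". Section 12.0 places the Frankl score at the end of each appointment. The Healthcare Provider Questionnaire is, under Section 10.0, "completed by the provider performing treatment". Its 1-10 items (Appendix A, Figure 4) cover cooperation, pain and anxiety; item 4 asks "How much anxiety do you think the child experienced".

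Section 12.0 describes the data capture: "The person viewing the video will record the verbally reported heart rate and at each step into the data collection sheet". The Section 9.0 calendar also lists scoring of behavior from the video. It names no separate scorer and does not say that the sound is off.

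**The concern.** Behavior is the primary objective (Section 2.1), and Frankl is the measure in the first hypothesis of Section 13.1. Heart rate is the measure in the second. The protocol has the person who rates the first attend to the second, and say it aloud, shortly before rating. A subjective score given with another outcome's value in mind can drift toward that value. Heart rate, Frankl and provider-rated anxiety may then point the same way partly because of the procedure and not because of the child.

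This matters in a pilot that reports only means and ranges (Sections 3.0 and 13.1), because readers will naturally look at whether the outcomes agree. Speaking the number may also affect the child, whose later heart rate is itself an outcome. Since the value has no stated clinical use, nobody in the operatory needs to hear it for the purposes the protocol gives.

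**Working it through.** The protocol states no figure for this point. The check is a trace of who knows the heart rate and what that person then scores, followed by a count.

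**Trace by rater**

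- *Provider.* Reads and speaks the value during each half (Section 3.0), then gives the Frankl score and the cooperation, pain and anxiety ratings (Sections 3.0 and 10.0; Appendix A, Figure 4). Under the Section 3.0 timing, that half's reading precedes its Frankl score. Under the Section 12.0 timing, both in-half readings do. Exposure is established either way.
- *Video viewer.* Hears and transcribes the value (Sections 3.0 and 12.0). Behavior is scored from the same video (Section 9.0). The viewer is exposed if the same person does both tasks, and any other scorer is exposed if the sound is on. Nothing in the protocol prevents either.
- *Child.* Is in the chair when the value is spoken. The calendar lists the FPS-R pain self-report under both conditions but does not place it relative to the announcement. Whether a child in the headset hears or understands the number is not stated. Exposure is possible.
- *Parent.* Section 8.2 provides for a parent who is not in the operatory. The parent surveys ask whether there was distress, how well pain and distress were managed, and about satisfaction; they contain no intensity score. Exposure is conditional and bears on less direct measures.

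**Count** (assuming one announcement per listed time point and 40 children completing both halves)

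- All announcements: 4 x 40 = 160.
- Readings taken inside a rated half: 2 x 40 = 80.
- The other 80 are 40 baseline and 40 post-operative readings. Baseline gives the provider a reference value but describes neither half. The post-operative reading follows the first half's Frankl score on the Section 3.0 schedule and may follow the second's.

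**Scale of a possible shift (illustration only)**

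The change in the mean VR-BBG Frankl difference is (net number of children moved one level) / 40. If 5% to 10% of children moved one level in the same direction:

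- 2 / 40 = 0.05
- 4 / 40 = 0.10

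The percentages are assumptions, because the protocol gives none. The sign could go either way, and movements in opposite directions would cancel. Entry is limited to Frankl 3 or 4 on a four-level scale (Sections 3.0 and 5.1), so the room for a true improvement is small.

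**The case against.** The strongest reply is that the provider sees the headset. Treatment is open to this rater, so the announcement reveals nothing about allocation. Frankl is a rating of observed behavior, and the protocol does not make heart rate an input to it. Anchoring would favor VR only if heart rate really is lower with VR; otherwise it adds noise without a fixed direction. No correlation or agreement analysis between heart rate and the ratings is stated. Filming the display also exchanges a dependable spoken record for one that can be lost.

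Much of this stands. A reader might infer that the announcement unblinds the rater or biases the trial toward VR; the protocol supports neither. A reader might also infer that everyone who scores the child knows the heart rate. That is established for the provider only. The parent may be absent, and neither the child's hearing of the value nor the timing of FPS-R is stated. Nor do all 160 announcements inform a rating of the half in which they are made; 80 do.

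What remains is that the stated procedure gives the rater of the main behavior measure the value of another outcome before rating. Open treatment does not excuse this, because it is a separate influence and an avoidable one. The absence of a planned agreement analysis does not remove it either, since means reported together will be compared.

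**Conclusion.** The point holds in a limited form. Heart rate is known to the provider before the Frankl score and the cooperation, pain and anxiety ratings, with 80 in-half announcements over 40 children. The spoken value is on the video used to score behavior, and the child, and a parent if present, may hear it. The consequence is loss of independence between outcomes and possible reactivity of the child. Direction and size are unknown; the 0.05 to 0.10 Frankl shift only shows what assumed rates would produce. This is a cheap improvement to measurement in a descriptive pilot. It is neither a contradiction in the protocol nor a wrong figure.

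The conclusion rests on the protocol's statement that heart-rate recording serves research only. If the display is in fact used in care, that statement must first be reconciled with practice.

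**What to change.** In Sections 3.0 and 12.0:

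- Remove the announcement. Place the pulse-oximeter display in the camera frame, out of the direct view of the provider, the child and, if present, the parent.
- Have the existing video viewer read heart rate from the display at the four defined time points.
- State that the provider completes the Frankl score and the questionnaire without seeing heart rate.
- In Section 9.0 or 12.0, state that behavior is scored from the video in one of three ways: before heart rate is transcribed, with the display masked, or by a different existing team member.

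Hiding the display from child and parent alone would not be enough, because the provider is the rater whose exposure is established. The change does not blind anyone to VR; the headset stays visible in the room and on the video.

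The cost is camera and monitor placement, a few lines of protocol text and some ordering of the video work, with no added staff. The downside is a lost reading if the display leaves the frame, so check the framing at baseline.
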